Following oral administration of olaparib via the capsule formulation, absorption is rapid with peak plasma concentrations typically achieved between 1 to 3 hours after dosing. On multiple dosing there is no marked accumulation (accumulation ratio of 1.4- 1.5 for twice daily dosing), with steady state exposure achieved within 3 to 4 days.

Co-administration with a high fat meal slowed the rate (Tmax delayed by 2 hours) of absorption, but did not significantly alter the extent of olaparib absorption (mean AUC increased by approximately 20%). Therefore there is no restriction with diet while olaparib is administered.

Drug interactions:

In vitro, olaparib was an inhibitor of CYP3A4 and an inducer of CYP2B6, but these activities occurred at higher concentrations than are clinically achieved. Olaparib produced little/no

A Phase II, Single-arm Study of Combination Pembrolizumab and Olaparib in the Treatment of Patients with Advanced Cholangiocarcinoma

Version 2.1: 17Mar2023

inhibitions of other CYP isozymes. In vitro studies have shown that olaparib is a substrate of CYP3A4.

Based on the data from a drug-interaction trial (N=57), the AUC and Cmax of Olaparib increased by 2.7- and 1.4-fold, respectively, when Olaparib was administered in combination with itraconazole, a strong CYP3A inhibitor. Simulations using physiologically-based pharmacokinetic (PBPK) models suggests that a moderate CYP3A inhibitor (fluconazole) may increase the AUC and Cmax of Olaparib by 2- and 1.1-fold, respectively.

Based on the data from a drug-interaction trial (N=22), the AUC and Cmax of Olaparib decreased by 87% and 71%, respectively, when Olaparib was administered in combination with rifampicin, a strong CYP3A inducer. Simulations using PBPK models suggested that a moderate CYP3A inducer (efavirenz) might decrease the AUC and Cmax of Olaparib by 50-60% and 20-30%, respectively.

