4.3.2.2 Effect of other drugs on olaparib

CYP3A4/5 are the isozymes predominantly responsible for the metabolic clearance of olaparib. Clinical studies conducted with a tablet formulation to evaluate the impact of known CYP3A inhibitors and inducers have shown that co-administration of a potent CYP3A inhibitor, itraconazole, increased olaparib Cmax by 142% (90% CI: 1.33-1.52) and increased mean AUC by 270% (90% CI: 2.44-2.97) and that co-administration of a potent CYP inducer, rifampicin, decreased Cmax by 71% (treatment ratio: 0.29; 90% CI: 0.24-0.33) and mean AUC by 87% (treatment ratio: 0.13; 90% CI: 0.11-0.16). Moderate inhibitors and inducers of CYP3A are also predicted to significantly alter the exposure of olaparib. It is therefore recommended that known strong CYP3A inhibitors (e.g., itraconazole, telithromycin, clarithromycin, boosted protease inhibitors, indinavir, saquinavir, nelfinavir, boceprevir, telaprevir) or moderate CYP3A inhibitors (ciprofloxacin, erythromycin, diltiazem, fluconazole, verapamil) should not be taken with olaparib.

If there is no suitable alternative concomitant medication then the dose of olaparib or study treatment should be reduced for the period of concomitant administration. With strong CYP3A inhibitors, the dose of olaparib tablet formulation should be reduced from 300 mg bid to 100 mg bid for the duration of concomitant therapy with the strong inhibitor and for 5 half-lives of the concomitant medication after stopping its treatment. With moderate CYP3A inhibitors, the dose of the tablet formulation should be reduced from 300 mg bid to 150 mg bid for the duration of concomitant therapy with the moderate inhibitor and for 3 half-lives of the concomitant medication

A Phase II, Single-arm Study of Combination Pembrolizumab and Olaparib in the Treatment of Patients with Advanced Cholangiocarcinoma

Version 2.1: 17Mar2023

after stopping its treatment. After the washout of the inhibitor is complete, the olaparib dose can be re-escalated.

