For further information, please refer to the Common Terminology Criteria for Adverse Events v4.0 (CTCAE) at <http://ctep.cancer.gov>

Dose Modification of Olaparib

Patients who experienced grade 3 or 4 toxicities attributable to Olaparib will temporarily hold Olaparib treatment until the side effects have improved to grade 1 or baseline, then restart Olaparib the next lower dose level.

Table 5: Olaparib Dose Modifications

Dose level -1	200 mg bid
Dose level -2	100 mg bid

A Phase II, Single-arm Study of Combination Pembrolizumab and Olaparib in the Treatment of

Patients with Advanced Cholangiocarcinoma

Version 2.1: 17Mar2023

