5.5.1 Acceptable Concomitant Medications

All treatments that the investigator considers necessary for a participant's welfare may be administered at the discretion of the investigator in keeping with the community standards of medical care. All concomitant medication will be recorded on the case report form (CRF) including all prescription, over-the-counter (OTC), herbal supplements, and IV medications and fluids. If changes occur during the trial period, documentation of drug dosage, frequency, route, and date may also be included on the CRF.

All concomitant medications received within 28 days before the first dose of trial treatment and 30 days after the last dose of trial treatment should be recorded. Concomitant medications administered after 30 days after the last dose of trial treatment should be recorded for SAEs and ECIs as defined in Section 7.2.

Considering olaparib treatment, avoid concomitant use of strong and moderate CYP3A inhibitors and consider alternative agents with less CYP3A inhibition. If the inhibitor cannot be avoided, reduce the olaparib dose to 150 mg twice daily for a strong CYP3A inhibitor or 200 mg twice daily for a moderate CYP3A inhibitor. (see FDA package insert of Olaparib).

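### Section 5.5.1 gives olaparib doses with an unavoidable CYP3A inhibitor that are 1.5 times (strong) and 1.33 times (moderate) those in Section 4.3.2.2

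*Combined protocol and SAP*

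**What the plan says.** Olaparib is given as tablets at 300 mg bid (Section 5.4, Table 2). Both relevant sections say that strong and moderate CYP3A inhibitors should be avoided, and both provide for the case where they cannot be.

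- **Section 5.5.1 (Acceptable Concomitant Medications):** "reduce the olaparib dose to 150 mg twice daily for a strong CYP3A inhibitor or 200 mg twice daily for a moderate CYP3A inhibitor". It refers to the FDA package insert and gives no period for keeping the lower dose after the inhibitor stops.
- **Section 4.3.2.2 (Effect of other drugs on olaparib), strong inhibitor:** "the dose of olaparib tablet formulation should be reduced from 300 mg bid to 100 mg bid", kept while the inhibitor is taken and "for 5 half-lives of the concomitant medication after stopping its treatment".
- **Section 4.3.2.2, moderate inhibitor:** "With moderate CYP3A inhibitors, the dose of the tablet formulation should be reduced from 300 mg bid to 150 mg bid", with a corresponding period of 3 half-lives.

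Flow chart footnote 6 (Section 6.1) directs sites to Section 5 for how olaparib and pembrolizumab are given. Section 4.3.2.2 lies in the background section.

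Separately, after a Grade 3 or 4 toxicity attributed to olaparib, the patient holds the drug and must "then restart Olaparib the next lower dose level". Those levels are 200 and 100 mg bid (Table 5, Olaparib Dose Modifications). Neither section on inhibitors prints a dose for a patient already at one of these levels. Section 4.3.2.2 says only in general that "the dose of olaparib or study treatment should be reduced for the period of concomitant administration".

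**The concern.** The same clinical situation has two different dosing rules in one protocol, and the rule that sites are pointed to is the more permissive one. The purpose of the adjustment is to offset the rise in exposure that the inhibitor causes. If the Section 5.5.1 doses offset it only in part, a patient on a strong or moderate inhibitor would have a higher olaparib AUC than on 300 mg bid alone. The protocol's tolerability statements stop at that dose (Sections 4.3.2.1 and 4.4.3).

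The effect is sharper for a patient already reduced for Grade 3 or 4 toxicity, because the inhibitor could cancel the benefit of the reduction. Section 5.5.1 also leaves out the post-inhibitor period, so a site reading that section alone could return to the former dose while inhibition persists.

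**Working it through.** **Inputs.** Section 4.3.1.1 (Drug interactions) reports from a drug-interaction trial that "the AUC and Cmax of Olaparib increased by 2.7- and 1.4-fold, respectively, when Olaparib was administered in combination with itraconazole", and from simulation that "a moderate CYP3A inhibitor (fluconazole) may increase the AUC and Cmax of Olaparib by 2- and 1.1-fold". Section 4.3.2.2 prints the itraconazole effect on AUC as an increase of 270% with a 90% CI of 2.44 to 2.97.

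**Check of the printed factor.** The geometric midpoint of the interval is √(2.44 × 2.97) = 2.69. The 270% is therefore a ratio of about 2.7, in line with Section 4.3.1.1, and not a 3.7-fold exposure.

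**Ratio of the two rules.** This needs no pharmacokinetic assumption:

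- strong: 150 / 100 = 1.5
- moderate: 200 / 150 = 1.33

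**AUC relative to 300 mg bid alone.** Assumption: human AUC is proportional to dose over 100 to 300 mg. The documents do not state this. Formula: adjusted dose × factor / 300.

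| Inhibitor | Section 4.3.2.2 | Section 5.5.1 |
|---|---|---|
| Strong (2.7) | 100 × 2.7 / 300 = 90% | 150 × 2.7 / 300 = 135% |
| Strong, over the 90% CI (2.44 to 2.97) | 81% to 99% | 122% to 149% |
| Moderate (2.0, simulated) | 150 × 2.0 / 300 = 100% | 200 × 2.0 / 300 = 133% |

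**Sensitivity to proportionality.** Let AUC vary as dose^b, with b from 0.8 to 1.2 (an illustrative range, not from the documents).

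- Section 5.5.1, strong: 0.5^b × 2.7 = 155% to 118%. Moderate: (2/3)^b × 2 = 145% to 123%.
- Section 4.3.2.2, strong: (1/3)^b × 2.7 = 112% to 72%. Moderate: 0.5^b × 2 = 115% to 87%.

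**Break-even factor.** At b = 1, the Section 5.5.1 moderate dose exceeds full-dose AUC only if the inhibitor's factor is above 300 / 200 = 1.5. The strong dose does so above 300 / 150 = 2.0.

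**Cmax relative to full dose**, with factors 1.4 and 1.1:

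- Section 5.5.1: 150 × 1.4 / 300 = 70% and 200 × 1.1 / 300 = 73%.
- Section 4.3.2.2: 100 × 1.4 / 300 = 47% and 150 × 1.1 / 300 = 55%.

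Peak concentration stays below full dose under either rule.

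**Patient already at 200 mg bid.** The Section 5.5.1 moderate dose is the dose already being taken. With a factor of 2.0, AUC doubles relative to the patient's own level, and no proportionality is needed because the dose is unchanged. With proportionality, that is again 133% of full-dose AUC, which is above the AUC at 300 mg bid from which the patient was reduced.

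**The case against.** **Which pair is right.** Section 5.5.1 cites the package insert, which is not available here. A reader might infer that its doses are proven wrong. The documents do not support that: they state no AUC ceiling, and restoring full-dose AUC is a criterion applied in this review. What stands is that the two pairs conflict, and that the protocol's own interaction data fit the Section 4.3.2.2 pair better. The label check therefore belongs in the fix.

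**Which section governs.** Footnote 6 points to Section 5, so sites are less likely to split between the two rules. That lessens the ambiguity, but it makes the higher doses the likely ones in practice.

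**Reach of the exposure figures.** A reader might infer that every strong or moderate inhibitor pushes AUC above full dose. The factors come from one strong inhibitor and one simulated moderate inhibitor. Section 4.3.2.2 names others, such as ciprofloxacin, diltiazem and verapamil, without factors. A moderate inhibitor below 1.5-fold would not exceed full-dose AUC.

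**Patients at 100 mg bid.** Both Section 5.5.1 doses, and the Section 4.3.2.2 moderate dose, lie above 100 mg bid. A reader might infer an instruction to escalate. There is none: both sections speak of reducing, and the general sentence in Section 4.3.2.2 covers these patients in principle. Only the number is missing.

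**Other safeguards.** The inhibitors are to be avoided in the first place, and the documents give no frequency for unavoidable use. The half-life periods do appear in Section 4.3.2.2, and the silence of Section 5.5.1 does not contradict them. Laboratory results must be acceptable before each dose of trial treatment (Section 7.1.3), and toxicity holds apply. These points limit the likely number and severity of events. However, the flow chart ties testing to the three-weekly pembrolizumab dose while olaparib is taken twice daily, so testing detects harm and does not prevent overexposure.

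**Conclusion.** The conflict is certain. Section 5.5.1 gives 1.5 times (strong) and 1.33 times (moderate) the dose recommended in Section 4.3.2.2 for the same full-dose patient.

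The exposure consequence is conditional. It rests on the itraconazole factor, a simulated fluconazole factor and assumed proportionality. On that basis Section 5.5.1 gives about 135% and 133% of full-dose AUC, against 90% and 100%. The excess persists over the itraconazole confidence interval and over the illustrative departures from proportionality.

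For a patient already at 200 mg bid, the Section 5.5.1 dose for a moderate inhibitor is no reduction at all.

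This is an inconsistency in the text with a safety consequence for a probably small number of patients, and it should be corrected. It should not be read as a threat to the trial's main result: the response endpoint and the error rates of the design are unaffected.

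**What to change.** Amend Section 5.5.1 as follows.

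1. Replace its doses with the Section 4.3.2.2 tablet doses (from 300 mg bid: 100 mg bid with a strong inhibitor, 150 mg bid with a moderate one), after checking them against the current tablet label. The protocol should then print one pair only.
2. Carry over the periods for keeping the lower dose after the inhibitor stops: 5 half-lives of the inhibitor (strong) and 3 (moderate).
3. State that the adjusted dose must never exceed the patient's current dose.
4. Have the clinical team set the doses for patients already at 200 or 100 mg bid under the olaparib dose-modification table. The arithmetic above is not a sufficient basis for those doses.

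The cost is a few sentences of protocol text, with no extra patients or procedures. The downside is a lower olaparib dose for a few patients while they take an inhibitor and during the washout.

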5.5.2 Prohibited Concomitant Medications

Participants are prohibited from receiving the following therapies during the Screening and Treatment Phase (including retreatment for post-complete response relapse) of this trial:

A Phase II, Single-arm Study of Combination Pembrolizumab and Olaparib in the Treatment of

Patients with Advanced Cholangiocarcinoma

Version 2.1: 17Mar2023

- Antineoplastic systemic chemotherapy or biological therapy
- Immunotherapy not specified in this protocol
- Chemotherapy not specified in this protocol
- Investigational agents other than pembrolizumab
- Radiation therapy
- Note: Radiation therapy to a symptomatic solitary lesion or to the brain may be allowed at the investigator's discretion.
- Live vaccines within 30 days prior to the first dose of study treatment and while participating in the study. Examples of live vaccines include, but are not limited to, the following: measles, mumps, rubella, varicella/zoster, yellow fever, rabies, BCG, and typhoid vaccine. Seasonal influenza vaccines for injection are generally killed virus vaccines and are allowed; however, intranasal influenza vaccines (e.g., FluMist®) are live attenuated vaccines and are not allowed.
- Systemic glucocorticoids for any purpose other than to modulate symptoms from an event of clinical interest of suspected immunologic etiology. The use of physiologic doses of corticosteroids may be approved after consultation with the Sponsor.

Participants who, in the assessment by the investigator, require the use of any of the aforementioned treatments for clinical management should be removed from the study. All treatments that the Investigator considers necessary for a participant's welfare may be administered at the discretion of the Investigator in keeping with the community standards of medical care.

Medications or vaccinations specifically prohibited in the exclusion criteria are not allowed during the ongoing study. If there is a clinical indication for any medication or vaccination specifically prohibited during the study, discontinuation from study therapy or vaccination may be required. The final decision on any supportive therapy or vaccination rests with the investigator and/or the participant's primary physician. However, the decision to continue the participant on study treatment requires the mutual agreement of the investigator, the Sponsor and the participant.

There are no prohibited therapies during the Post-Treatment Follow-up Phase.

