9. Has known active central nervous system (CNS) metastases and/or carcinomatous meningitis. Subjects with previously treated brain metastases may participate provided they are stable (without evidence of progression by imaging for at least four weeks prior to the first dose of trial treatment and any neurologic symptoms have returned to baseline), have no evidence of new or enlarging brain metastases, and are not using steroids for at least 7 days prior to trial treatment. This exception does not include carcinomatous meningitis, which is excluded regardless of clinical stability.
10. Has active autoimmune disease that has required systemic treatment in the past 2 years (i.e. with use of disease modifying agents, corticosteroids, or immunosuppressive drugs). Replacement therapy (e.g., thyroxine, insulin, or physiologic corticosteroid replacement therapy for adrenal or pituitary insufficiency, etc.) is not considered a form of systemic treatment.
11. Has known history of, or any evidence of active, non-infectious pneumonitis.
12. Has an active infection requiring systemic therapy.
13. Has a history or current evidence of any condition, therapy, or laboratory abnormality that might confound the results of the trial, interfere with the subject's participation for the full

A Phase II, Single-arm Study of Combination Pembrolizumab and Olaparib in the Treatment of Patients with Advanced Cholangiocarcinoma

Version 2.1: 17Mar2023

duration of the trial, or is not in the best interest of the subject to participate, in the opinion of the site investigator.

14. Has known psychiatric or substance abuse disorders that would interfere with cooperation with the requirements of the trial.
15. Is pregnant or breastfeeding, or expecting to conceive or father children within the projected duration of the trial, starting with the pre-screening or screening visit through 120 days after the last dose of trial treatment.
16. Has received prior therapy with an anti-PD-1, anti-PD-L1, or anti-PD-L2 agent.
17. Has a diagnosis of immunodeficiency or is receiving chronic systemic steroid therapy (in dosing exceeding 10 mg daily of prednisone equivalent) or any other form of immunosuppressive therapy within 7 days prior to the first dose of study drug.

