5.5 Concomitant Medications/Vaccinations (allowed & prohibited)

Medications or vaccinations specifically prohibited in the exclusion criteria are not allowed during the ongoing trial. If there is a clinical indication for one of these or other medications or vaccinations specifically prohibited during the trial, discontinuation from trial therapy or vaccination may be required. The final decision on any supportive therapy or vaccination rests with the investigator and/or the participant's primary physician.

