5.6 Participant Withdrawal/Discontinuation Criteria

Participants may discontinue study treatment at any time for any reason or be dropped from the study treatment at the discretion of the investigator should any untoward effect occur. In addition, a participant may be discontinued from study treatment by the investigator or the Sponsor if study treatment is inappropriate, the trial plan is violated, or for administrative and/or other safety reasons. Specific details regarding procedures to be performed at study treatment discontinuation are provided in Section 7.1.4 – Other Procedures.

A participant must be discontinued from study treatment but continue to be monitored in the study for any of the following reasons:

- The participant or participant's legally acceptable representative requests to discontinue study treatment
- Confirmed radiographic disease progression outlined in Section 7.1.2.6
- Any progression or recurrence of any malignancy, or any occurrence of another malignancy that requires active treatment
- Unacceptable adverse experiences as described in Section 5.2.2.
- The participant has a medical condition or personal circumstance that, in the opinion of the investigator and/or sponsor, placed the participant at unnecessary risk from continued administration of study treatment.
- The participant has a confirmed positive serum pregnancy test
- Noncompliance with study treatment or procedure requirements

A Phase II, Single-arm Study of Combination Pembrolizumab and Olaparib in the Treatment of

Patients with Advanced Cholangiocarcinoma

Version 2.1: 17Mar2023

- Recurrent Grade 2 pneumonitis
- Discontinuation of treatment may be considered for participants who have attained a confirmed complete response (CR) and have been treated for at least 8 cycles (at least 24 weeks), receiving 2 doses of pembrolizumab and at least 80% of the planned doses of olaparib beyond the date when the initial CR was declared. These participants may be eligible for second course treatment described in Section 5.2.3.
- The participant is lost to follow-up
- Completion of 35 treatments (approximately 2 years) with pembrolizumab

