7.1.5.3 Survival Follow-up

Participants who experience confirmed disease progression or start a new anticancer therapy, will move into the Survival Follow-Up Phase and should be contacted by telephone every 12 weeks to assess for survival status until death, withdrawal of consent, or the end of the trial, whichever occurs first.

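### Section 5.5.2 removes from the study anyone who needs a prohibited treatment while on therapy, but the rest of the protocol keeps such patients in follow-up; read literally, it loses survival, some progression and some safety data, probably in a minority of patients.

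*Combined protocol and SAP*

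**What the plan says.** Section 5.5.2 lists therapies prohibited in the Screening and Treatment Phase. They include other systemic anticancer therapy, other investigational agents, radiation, live vaccines, and systemic glucocorticoids except for suspected immune-related events of clinical interest. A note adds that "Radiation therapy to a symptomatic solitary lesion or to the brain may be allowed" at the investigator's discretion. The section then says that participants who, in the investigator's assessment, "require the use of any of the aforementioned treatments for clinical management should be removed from the study".

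Other passages give the same patient a different route:

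- **5.5.2, next paragraph:** where a prohibited medication is indicated, "discontinuation from study therapy or vaccination may be required". Continuing study treatment needs the agreement of investigator, sponsor and participant, so even staying on treatment is contemplated.
- **5.5.2, last line:** "There are no prohibited therapies during the Post-Treatment Follow-up Phase".
- **5.5:** "discontinuation from trial therapy or vaccination may be required".
- **5.6:** "A participant must be discontinued from study treatment but continue to be monitored in the study for any of the following reasons".
- **7.1.5.3:** "Participants who experience confirmed disease progression or start a new anticancer therapy, will move into the Survival Follow-Up Phase", with calls every 12 weeks until death, withdrawal of consent or the end of the trial. Section 7.1.1.5.3 likewise sends patients who start new anticancer therapy to survival follow-up.
- **7.1.5.2:** patients who stop treatment for a reason other than progression go on to imaging follow-up.

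**The concern.** Leaving treatment and leaving the study are different events for the data. The first keeps a patient in the time-to-event and safety analyses. The second ends observation. Section 5.5.2 uses the language of the second where the other sections use that of the first, and no passage says that the two mean the same here.

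An on-treatment need for radiation, non-exempt steroids or other anticancer therapy plausibly marks worsening disease or toxicity. (A live vaccine does not.) If those patients are censored at that moment, their later risk is likely to be higher than that of the patients who remain, and Kaplan-Meier estimates of PFS and OS may be biased upward. Serious adverse events after removal would no longer be actively sought.

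**Working it through.** The plan gives no figure on this point, so the check traces patients through the sections and then illustrates the possible effect.

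**1. Who is caught, and what is lost**

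- *Not progressed, needs radiation outside the two exceptions in the note.* 5.5.2 removes the patient. If study treatment stops, 7.1.5.2 would image every 6 weeks (every 9 after one year). Removal loses later progression, death, and active SAE follow-up to 90 days after treatment (7.2).
- *Systemic steroids for a Grade 3 or 4 infusion reaction.* Table 4 lists corticosteroids for this and permanently discontinues study drug. Section 9.1.1.1.7 says infusion reactions are not considered immune mediated, so the steroid exemption in 5.5.2 does not clearly apply. Read literally, care listed in the protocol itself triggers removal, with the same losses.
- *Other anticancer therapy needed while on treatment.* 7.1.5.3 provides survival calls. Imaging would stop anyway under 7.1.5.2. Removal loses OS, death as a PFS event if the patient has not progressed, and active SAE follow-up to 30 days after treatment.
- *Treatment stopped for confirmed progression, chemotherapy afterwards.* Not caught: the prohibition covers only the Screening and Treatment Phase. Nothing is lost.

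**2. How the analysis would treat a removed patient**

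PFS is censored at the last disease evaluation (4.5.2). For OS, censoring is stated only for patients alive at the end of the study (8.1.1.2), so no OS rule covers removal. Both endpoints are analysed by Kaplan-Meier (8.2.2), which assumes that censored patients have the same future risk as those still followed.

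**3. Illustration of the bias**

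Inputs from the plan: the benchmarks of 40 weeks for OS and 24 weeks for PFS (3.2). Assumptions, because the documents give neither: a fraction f of patients is removed, each 6 or 12 weeks before the event; event times are exponential with true medians at the benchmarks.

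Hand check: if a fraction f of events is replaced by censoring just before the event, the observed hazard falls from λ to (1 − f)λ, and the apparent median is the true median / (1 − f).

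- OS: 40/0.95 = 42.1; 40/0.90 = 44.4; 40/0.80 = 50.0; 40/0.70 = 57.1 weeks.
- PFS: 24/0.95 = 25.3; 24/0.90 = 26.7; 24/0.80 = 30.0; 24/0.70 = 34.3 weeks.

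Simulated Kaplan-Meier medians (400,000 patients per setting; the two values are for removal 6 and 12 weeks before the event):

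| f | f × 36 | OS, weeks | PFS, weeks |
|---|---|---|---|
| 0 | 0 | 39.9 / 40.1 | 23.9 / 24.0 |
| 5% | 1.8 | 41.9 / 41.8 | 25.0 / 24.9 |
| 10% | 3.6 | 44.0 / 43.6 | 26.2 / 25.9 |
| 20% | 7.2 | 49.1 / 48.1 | 29.0 / 28.2 |
| 30% | 10.8 | 55.4 / 53.9 | 32.8 / 31.1 |

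The simulation agrees with the hand check, which is its limit as the lead time goes to zero. The setting is unfavourable by construction: every removal comes shortly before an event. The PFS column also treats every removed patient as not yet progressed, so it overstates the effect on PFS. Removal unrelated to prognosis would cost precision but cause no systematic bias.

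**The case against.** The strongest reply is that this is loose wording which the rest of the protocol corrects. Survival follow-up is provided for, nothing is prohibited after treatment, and a sensible site would read removal as removal from treatment. PFS and OS are secondary estimates with no planned test. That limits the consequence. It does not remove the conflict, because a site can only guess which instruction governs.

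Several stronger readings are tempting, and the documents do not support them:

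- *Most patients who progress go on to chemotherapy, so few deaths would be observed.* The prohibition ends with the treatment phase, and 5.6 and 7.1.5.3 keep progressed patients under observation.
- *PFS is lost for everyone removed.* Patients who have progressed already have their event, and disease-status imaging stops at new anticancer therapy in any case.
- *Late immune toxicity is missed.* Steroids for suspected immune events are exempt, 7.1.4.1 requires events present at withdrawal to be followed, and 7.2 keeps drug-related SAEs reportable whenever they reach the investigator. What is lost is active follow-up: 7.2 does not oblige investigators to seek events in former participants.
- *Three or four removals would use up the 10% drop-out allowance.* That count is not in the documents, and the allowance sizes the response-rate test (8.1.1.3), not survival follow-up.
- *The radiotherapy note contradicts the removal sentence.* It reads naturally as an exception, although the text does not say so.
- *Exclusion 17 in 5.3 admits patients on up to 10 mg prednisone equivalent daily, whom 5.5.2 then bars.* Exclusion 17 is an entry threshold, not permission to continue, and 5.5.2 lets the sponsor approve physiologic doses.

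It is also fair to say that 5.6 does not list needing a prohibited treatment. It reaches these patients only through other reasons, such as progression, a medical condition or noncompliance.

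**Conclusion.** The conflict is real and lies in the text, including within 5.5.2 itself. Applied literally, the sentence ends OS follow-up, PFS follow-up in patients not yet progressed, and active SAE follow-up in the 90-day (or 30-day) window. This applies to patients who need a listed, non-exempt treatment while on therapy. The resulting censoring may be informative and may bias PFS and OS upward.

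The size cannot be fixed from the documents, and the group is probably a minority. Under the stated assumptions, 5% to 10% removed would move a 40-week median OS to about 42 to 44 weeks. The 20% and 30% rows only show how the effect grows. The link between needing these treatments and prognosis is a plausible inference that the documents do not test.

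**What to change.** Reword the sentence in 5.5.2 so that it governs follow-up status only: whatever is decided about study treatment, the participant stays in the study for the safety, disease-status and survival follow-up scheduled in 6.1 and 7.1.5, unless consent is withdrawn.

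Separately, the sponsor should reconcile 5.5.2 with 5.5, with 5.6, and with its own radiotherapy and steroid exceptions on when study treatment stops. No clinical rule is proposed here.

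The cost is a short protocol amendment. It adds no type of visit, and the sample size and the response-rate decision rule do not change.
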